12 ADVERSE EVENT REPORTING AND CRITERIA

12.1 DEFINITION OF ADVERSE EVENT

An AE is any untoward medical occurrence in a clinical investigation subject administered a pharmaceutical product. An AE does not necessarily have to have a causal relationship with this treatment. An AE can therefore be any unfavorable and unintended sign (including an abnormal laboratory finding, for example), symptom, or disease temporarily associated with the use of a medicinal product, whether or not considered related to the medicinal product. This includes any occurrence that is new in onset or aggravated in severity or frequency from the baseline condition. An AE can occur at any time, including during screening, run-in or washout periods, even if no study treatment has been administered. It is the responsibility of the Investigator, based on their knowledge and experience, to determine which untoward medical occurrences should be considered AEs.

12.2 CRITERIA FOR SERIOUS ADVERSE EVENTS (SAE)

The definitions of SAEs are described below. The Investigator is responsible for ensuring that all staff involved in the study are familiar with the content of this section.

An SAE or reaction is defined as any untoward medical occurrence that meets at least one of the following criteria:

• Results in death:

In the case of deaths, the event(s) leading to the death should be recorded and reported as SAE(s) with the outcome "Fatal". The death itself will not be reported as an SAE, unless the cause of the death is unknown (e.g., in case of unexplained or sudden death);

• Is life-threatening:

The term "life-threatening" refers to an event in which the subject is at immediate risk of death at the time of the event; it does not refer to an event which hypothetically might cause death if it was more severe;

- Requires inpatient hospitalization or prolongation of existing hospitalization;
- Results in persistent or significant disability/incapacity;

A disability is defined as any substantial disruption of a subject's ability to conduct normal life functions;

- Is a congenital anomaly/birth defect; and/or
- Is medically important.

Medical and scientific judgement must be exercised in deciding whether an AE is considered "medically important". Medically important events may not be immediately life-threatening or result in death or hospitalization but may jeopardize the subject or may require intervention to prevent one of the other outcomes listed in this definition. Examples of such events are intensive treatment in an emergency room or at home for allergic bronchospasm; blood dyscrasias or convulsions that do not result in hospitalization; or development of drug dependency or drug abuse.

U2-VEN-207

Progression of disease (including fatal outcomes), if documented by use of appropriate method (for example, as per IWCLL Hallek et al., 2018), should not be reported as a SAE.

Situations Not Considered SAEs:

Treatment within or admission to the following facilities is not considered to meet the criteria of "inpatient hospitalization" (although if any other SAE criteria are met, the event must still be treated as an SAE and immediately reported i.e., could meet the definition of important medical event):

- Emergency Department or Emergency Room;
- Hospitalization for drug administration, diagnostic procedure, or social circumstances;
- Outpatient or same day surgery units;
- Observation or short-stay unit;
- Rehabilitation facility;
- Hospice or skilled nursing facility;
- Nursing homes, Custodial care or Respite care facility.

Hospitalization during the study for a pre-planned surgical or medical procedure (one which was planned prior to entry in the study), does not require reporting as an SAE to the Sponsor, but if hospitalization is prolonged due to an event this would be reportable to Sponsor or designee.

Serious Versus Severe AEs:

It is important to distinguish between "serious" and "severe" AEs, as the terms are not synonymous. Severity is a measure of intensity; however, an AE of severe intensity need not necessarily be considered serious. For example, nausea which persists for several hours may be considered severe nausea but may not be considered an SAE. On the other hand, a stroke which results in only a limited degree of disability may be considered only a mild stroke but would be considered an SAE. Severity and seriousness should be independently assessed when recording AEs and SAEs on the eCRF.

12.2.1 ADVERSE EVENT/SERIOUS ADVERSE EVENT GRADING

The NCI CTCAE v5.0 is to be used for the grading of severity of AEs.

For AEs not covered by the NCI CTCAE grading system, the following definitions should be used:

- **Grade 1**: Mild; asymptomatic or mild symptoms; clinical or diagnostic observations only; intervention not indicated;
- **Grade 2:** Moderate; minimal, local or non-invasive intervention indicated; limiting age appropriate instrumental ADL*;
- **Grade 3**: Severe or medically significant but not immediately life-threatening; hospitalization or prolongation of hospitalization indicated; disabling; limiting self-care ADL**;
- **Grade 4**: Life-threatening consequences; urgent intervention indicated;
- **Grade 5**: Death related to AE.

U2-VEN-207

Activities of Daily Living (ADL)

*Instrumental ADL refer to preparing meals, shopping for groceries or clothes, using the telephone, managing money, etc.

**Self-care ADL refer to bathing, dressing and undressing, feeding self, using the toilet, taking medications, and not bedridden.

12.2.2 ADVERSE EVENTS / SERIOUS ADVERSE EVENT CAUSALITY ASSESSMENT

The Investigator must also assess the causal relationship of any AE to the study drug(s) (whether no study drug, monotherapy or combination therapy was administered), based on available information, using the following guidelines:

- **Not Related**: Clear cut temporal and/or mechanistic relation to a cause other than the study drug(s)
- **Doubtful**: There is no reasonable possibility that the event is related to the study drug(s) but a definite cause cannot be ascertained
- **Possible**: There is still a reasonable possibility that the cause of the event was the study drug(s) but there exists a more likely cause of the event such as complications of progressive disease
- **Probable**: The most likely cause of the event is the study drug(s) but other causes cannot be completely excluded
- **Definite:** Clear cut temporal and/or mechanistic relation to the study drug(s). All other causes have been eliminated. Events classified as definite will often be confirmed by documenting resolution on discontinuation of the study drug and recurrence upon resumption

12.2.3 ADVERSE EVENT/SERIOUS ADVERSE EVENT RECORDING

All non-serious AEs regardless of relationship to the study drugs are to be recorded on the eCRF from Cycle 1/Day 1 until 30 days after discontinuation or completion of protocol-specific treatment. Immune-related AE (irAEs) are to be recorded on the eCRF from Cycle 1/Day 1 until 90 days after study discontinuation or completion of protocol-specific treatment. All AEs must include the Investigator's assessment of the event's seriousness, severity, and causality to study drug.

All serious AEs (i.e. SAEs) regardless of relationship to the study drug(s) are to be recorded on the eCRF and the SAE Report Form from signing of informed consent until 30 days after discontinuation or completion of protocol-specific treatment. Immune-related SAEs (irSAEs) are to be recorded on the eCRF and SAE Report Form from signing of informed consent until 90 days after study discontinuation or completion of protocol-specific treatment. All SAEs must include the Investigator's assessment of the event's seriousness, severity, and causality to study drug.

If an AE is deemed by the Investigator as serious, as per the SAE criteria, it should be reported **as soon as possible and no later than 24 hours** of awareness to the Sponsor or designee using the SAE Report Form and recorded within the same timeframe on the eCRF. Follow-up information for SAEs and information on non-serious AEs that become serious should also be reported **as soon as possible but no later than 24 hours** to the Sponsor or designee using the SAE Report Form and recorded on the eCRF. SAEs should be followed until resolution (including results of an autopsy report, if applicable). The Investigator must review and sign off on the data on the SAE Report Form

U2-VEN-207

and transmission of the SAE Report Form should be confirmed by the site personnel submitting the form.

Disease progression or death due to disease progression should be reported by the Investigator as a SAE **only** if it is assessed that the study drugs caused or contributed to the disease progression (i.e., by a means other than lack of effect). Unrelated events of CLL/SLL progression should be captured on the appropriate eCRF and not on the AE eCRF.

Other untoward events occurring in the framework of the study are also to be recorded as AEs (i.e., AEs that occur prior to assignment of study drug that are related to a protocol-mandated intervention, including invasive procedures such as biopsies, medication washout, or no treatment run-in).

All AEs (non-serious and serious) resulting in discontinuation should be followed until resolution or stabilization of the event for up to 30 days (for any AEs/SAEs) or 90 days (for irAEs/irSAEs) as part of the study follow-up period. All new AEs (non-serious and serious) occurring during the follow-up period must be reported and followed until resolution unless, in the Investigator's judgement, these are not likely to improve due to the underlying disease.

After the 30-day (for any AEs/SAEs) or 90-day (for irAEs/irSAEs) follow-up period, only AEs and SAEs, which include death, assessed by the Investigator as drug-related are to be reported in the eCRF or SAE Report Form, as applicable.

After this period, investigators should report any deaths, serious adverse events, or other adverse events of concern that are believed to be related to prior treatment with study drug.

Investigators must report SAEs and follow-up information to their responsible IRBs/Independent Ethics Committee (IEC) according to the policies of the responsible IRB/IEC.

Investigators should use correct medical terminology/concepts and avoid colloquialisms and abbreviations when recording AEs or SAEs on the eCRF and/or SAE Report Form.

12.2.3.1 ABNORMAL LABORATORY VALUES, PHYSIOLOGICAL RESULTS, AND VITAL SIGNS

Abnormal laboratory values, physiological test results (e.g., QTc prolongation in electrocardiogram [ECG]), or vital signs should not be reported as an AE unless any criterion for an SAE is fulfilled, if it results in the subject to discontinue study drug, if it is associated with an overdose, or in the Investigator's judgement the abnormality should be reported as an AE.

If an abnormal finding is associated with a clinical sign and/or symptom, the sign or symptom should be reported as an AE, and the associated laboratory value or vital sign should be considered additional information that must be collected in the relevant eCRF. If the laboratory abnormality is a sign of a disease or syndrome, only the diagnosis needs to be recorded on the SAE Report Form or AE eCRF.

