8.5.3.3 DOSE HOLD/MODIFICATION: VENETOCLAX

Supportive care should be considered for any subject who experiences $Grade \ge 2$ cytopenias, or $Grade \ge 1$ non-hematologic toxicities. If a subject experiences a treatment-related AE requiring dose modification during the course of therapy, then study drug administration should be held, as necessary, until the AE resolves or stabilizes to an acceptable degree. In addition, the subject should be notified of the change in dose and the appropriate clinic staff should instruct the subject about the revised number of study medication tablets to be used per dose according to the new dose level. Any questions regarding dose modification should be referred to TG Therapeutics. Please see Table 22 for further guidance.

U2-VEN-207

If a subject discontinues only one study drug, the subject may continue treatment with the other study drug(s) per the protocol.

TABLE 20. DOSE MODIFICATIONS OF VENETOCLAX BASED ON LABORATORY PARAMETERS

Event	Occurrence	Action	
Tumor Lysis Syndrome			
Blood chemistry	Any	Withhold the next day's dose. If resolved within 24 to 48	
changes or		hours of last dose, resume at the same dose.	
symptoms		For any blood chemistry changes requiring more than 48	
suggestive of		hours to resolve, resume at reduced dose.	
TLS		For any events of clinical TLSa, resume at a reduced dose	
		following resolution.	
^a Clinical TLS is laboratory TLS with clinical consequences such as acute renal failure, cardiac			
arrhythmias, or sudden death and/or seizures.			

Please refer to the US prescribing information (https://www.accessdata.fda.gov/drugsatfda_docs/label/2018/208573s009lbl.pdf) and www.venetoclax.com for the most up to date information including warnings and precautions, adverse reactions, and boxed warnings.

TABLE 21: DOSE MODIFICATION FOR TOXICITY DURING VENETOCLAX

Dose at Interruption, mg	Restart Dose Reduction, mg	
400	300	
300	200	
200	100	
100	50	
50	20	
20	10	
During the ramp-up phase, continue the reduced dose for 1 week before increasing the dose.		

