8.5.4 DOSE HOLD/MODIFICATION: UBLITUXIMAB, UMBRALISIB AND VENETOCLAX

Table 22 illustrates the dose hold and modifications for all investigational products in the present study.

Subjects should be assessed clinically for toxicity at each visit using the NCI CTCAE v5.0 (https://ctep.cancer.gov/protocoldevelopment/electronic_applications/docs/ctcae_v5_quick_reference_5x7.pdf) grading scale.

Dose hold and/or modification guidance is for adverse events considered *related* to the study drug(s). If the adverse event is *not considered related* to a study drug (ublituximab, umbralisib and/or venetoclax), then that drug does not need to be modified or held as per Investigator assessment.

If cytopenias are deemed related to the underlying disease rather than study drug, dose modifications are not required, or are per investigator discretion. If a subject discontinues one or more study drugs, the subject may continue treatment with the other study drug(s) per the protocol.

U2-VEN-207

Dose reduction and/or holds are permitted as per Investigator discretion to manage adverse events related to one or more of the study drugs. The guidelines below are recommendations and are not meant to replace Investigator discretion.

TABLE 22. STUDY DRUG MODIFICATIONS

	Ublituximab	Umbralisib	Venetoclax	
NCI CTCAE Grade				
Neutropenia				
Grade 1-2 neutropenia	Maintain full dose. Consider growth- factor support as warranted.	Maintain current dose. Consider growth-factor support as warranted.	Maintain current dose. Consider growth-factor support as warranted.	
Grade 3 neutropenia	Maintain full dose. For recurrent or persistent Grade 3 neutropenia hold ublituximab until Grade ≤2, then resume. Consider growth- factor support as warranted.	Maintain current dose. If recurrence or persistent Grade 3, hold umbralisib until Grade ≤ 2 and resume at same dose. Consider growth-factor support as warranted.	Maintain current dose, if Grade 3 recurs or is persistent then hold venetoclax until ≤ Grade 2, after resume at the same dose. Consider growth-factor support as warranted.	

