Grade 4 neutropenia or occurrence of Neutropenic fever or infection	Hold ublituximab until Grade ≤ 3 and/or neutropenic fever or infection is resolved; consider growth factor support as warranted; thereafter, resume at full dose	Hold umbralisib until Grade ≤3 and/or neutropenic fever or infection is resolved; thereafter, resume umbralisib at current dose. Consider growth- factor support as warranted. If recurrence after rechallenge despite maximum supportive care, hold umbralisib until ≤ Grade 3; thereafter resume umbralisib at next lower dose level.	Hold venetoclax until Grade ≤3 and/or neutropenic fever or infection is resolved; thereafter, resume venetoclax at current dose. Consider growth- factor support as warranted. If recurrence after rechallenge despite maximum supportive care, hold venetoclax until ≤ Grade 3; thereafter resume venetoclax at next lower dose level.	
Thrombocytopenia				

U2-VEN-207

	Ublituximab	Umbralisib	Venetoclax	
	Ublituximab	Umbralisib	Venetoclax	
Grade 3 thrombocytopenia	Maintain full dose.	Maintain current dose.	Maintain current dose.	
Grade 4 thrombocytopenia	Hold ublituximab until Grade ≤ 3; thereafter resume at full dose.	Hold umbralisib until Grade ≤3; thereafter, resume umbralisib at current dose. If recurrence after rechallenge despite maximum supportive care, hold umbralisib until ≤ Grade 3; thereafter resume umbralisib at next lower dose level.	Hold venetoclax until Grade ≤3; thereafter, resume venetoclax at current dose. If recurrence after rechallenge despite maximum supportive care, hold venetoclax until ≤ Grade 3; thereafter resume venetoclax at next lower dose level.	
Infection (including opportunistic infection)				
	Ublituximab	Umbralisib	Venetoclax	
Grade 2 infection	Consider dose hold and/or supportive care as per investigator discretion.	Consider dose hold and/or supportive care as per investigator discretion.	Consider dose hold and/or supportive care as per investigator discretion.	
Grade 3 or 4 infection	Withhold ublituximab until resolved, then resume at full dose.	Withhold umbralisib until resolved, then resume at same or reduced dose.	Withhold venetoclax until resolved, then resume at same or reduced dose.	

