11.9 SAFETY ANALYSES

Safety analyses will be performed using the safety population. Safety analyses will be primarily based on the incidence, severity, and type of AEs, as well as on clinically meaningful laboratory results, physical examination, and vital signs as available. Safety variables will be tabulated and presented by the dose of ublituximab, umbralisib, and/or venetoclax actually received. Exposure to study treatment and reasons for discontinuation of study treatment will also be tabulated.

Detailed information collected for each AE will be included in a listing: AE term, start/stop dates of the AE, seriousness, severity, relationship to study drug(s), action taken, and outcome. In addition, the number and percentage of subjects experiencing at least one treatment-emergent AE will be tabulated by body system, preferred term, and CTCAE grade. Treatment-emergent AEs, drug-related AEs, AESIs, SAEs, AEs with a fatal outcome, and AEs leading to discontinuation/dose modification will be further summarized. Summary statistics for actual values and for changes from baseline will be tabulated for clinical laboratory results by scheduled visit. Subjects with laboratory values outside of the normal reference range at any post-baseline assessment will be summarized and graded per NCI CTCAE Version 5.0 as applicable. Subject incidence of abnormal laboratory results will be summarized by treatment group and maximum grade for each abnormal laboratory finding.

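### Section 12.2.3.1 does not require a laboratory abnormality that causes a dose hold or reduction to be reported as an AE, so the AE-based summaries that depend on it may be incomplete

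*Combined protocol and SAP*

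**What the plan says.** **Reporting rule (12.2.3.1).** The rule covers abnormal laboratory values, physiological results and vital signs. Such a finding is to "not be reported as an AE unless any criterion for an SAE is fulfilled, if it results in the subject to discontinue study drug". The same sentence adds two more exceptions: "if it is associated with an overdose", or where in the Investigator's "judgement the abnormality should be reported as an AE". The next paragraph gives a symptom route and a diagnosis route: "If the laboratory abnormality is a sign of a disease or syndrome, only the diagnosis needs to be recorded".

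**Dosing sections (8.5.2.2, 8.5.3.3, 8.5.4).** Section 8.5.4 opens its table with "Dose hold and/or modification guidance is for adverse events considered" related to study drug. Sections 8.5.2.2 and 8.5.3.3 likewise speak of treatment-related AEs that require a dose modification. Many of the events are laboratory findings. In Table 20, one venetoclax rule begins "For any blood chemistry changes requiring more than 48" hours to resolve and leads to a reduced dose. In Table 22, recurrent Grade 4 neutropenia or thrombocytopenia leads to a hold and then "thereafter resume umbralisib at next lower dose level", with a parallel entry for venetoclax.

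**Analysis (11.9).** Drug-related AEs are to be summarized, and "AEs with a fatal outcome, and AEs leading to discontinuation/dose modification will be further summarized". The AE listing carries relationship to study drug and action taken.

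**The concern.** Three parts of the protocol treat the same event differently. The dosing sections call a laboratory-driven hold or reduction a response to a related adverse event. The reporting section says not to report a laboratory abnormality unless an exception applies, and dose modification is not one. The analysis section then tabulates AEs that led to dose modification, which presumes that they were reported.

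At stake is the attribution of toxicity. Cytopenias, chemistry changes of tumor lysis and transaminase rises are among the events the protocol itself plans to manage by dose changes. Whether each becomes an AE record, with a causality assessment and an action taken, rests on individual judgement at up to 125 sites where the arm is known. The DSMB reviews AEs and SAEs under Section 13.1, so its AE data share the gap.

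**Working it through.** The plan states no figure on this point, so the check is to take typical events through the rule and then see what each planned output would hold.

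**Step 1: events against the exceptions in 12.2.3.1**

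| Event, with no admission and no permanent discontinuation | Action in the protocol | Reporting trigger met without judgement? |
|---|---|---|
| Asymptomatic Grade 4 neutropenia that recurs after rechallenge | Hold, then lower umbralisib or venetoclax dose (Table 22) | No. An AE if the Investigator so judges; an SAE if judged medically important |
| Grade 4 thrombocytopenia that recurs after rechallenge | Same pattern (Table 22) | No, as above |
| Asymptomatic Grade 3 or higher liver enzyme rise | Umbralisib resumed at a lower level after recovery (Table 22) | No, as above |
| TLS-type chemistry change lasting over 48 hours | Reduced venetoclax dose (Table 20) | No, unless a diagnosis of TLS is made |
| Any of these, with study drug discontinued | Discontinuation | Yes |

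**Step 2: what each output holds**

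- *AE-based summaries (11.9):* event term, relationship and action taken, but only for events that were reported.
- *Exposure summary (11.7):* number and percentage of subjects with a modified dose, by type and cycle. It does not depend on AE reporting. As described, it gives no event and no causality.
- *Graded laboratory tables (11.9):* out-of-range values by CTCAE grade, with incidence by treatment group and maximum grade. They do not depend on AE reporting either. As described, they give no causality and no action taken.
- *Phase 3 stopping rules (11.11.5):* these count treatment-related Grade 5 events and discontinuations of all therapies. Death is an SAE criterion and discontinuation is an exception in 12.2.3.1, so this gap does not touch them.

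Only the AE-based summaries are exposed. The other two outputs hold the pieces but not the link between them.

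**Step 3: what could be said about size**

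Let p be the proportion of subjects in an arm with a non-serious laboratory abnormality causing a hold or reduction, and r the proportion of these reported as AEs. The reported proportion is r × p.

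- Difference between arms as reported: r_A × p_A − r_B × p_B.
- If r is the same in both arms, the difference becomes r × (p_A − p_B) and the ratio p_A / p_B is unchanged.
- If r differs by arm, the ratio is multiplied by r_A / r_B, which may be above or below 1.

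None of p_A, p_B, r_A or r_B is in the documents. Each r can lie anywhere from 0 to 1, so neither the size nor the direction of any distortion can be derived.

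**The case against.** The strongest reply is that the sections can be read together. Section 12.1 counts an abnormal laboratory finding as a possible AE. An Investigator who applies Table 22 has, by the opening of 8.5.4, already regarded the event as a related AE, so the judgement exception should follow. Section 12.2 names blood dyscrasia without admission as an example of a medically important event, so some cases would qualify as SAEs. Tumor lysis has the diagnosis route. The laboratory tables cover any post-baseline assessment, and a value that caused a hold was, by definition, measured. Section 13.1 also gives the DSMB safety trends, and the synopsis has it review safety data. A separate SAP or eCRF guideline might settle the matter.

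Much of this stands, and it rules out a stronger reading. A reader might infer that these abnormalities are lost from the AE data and from the dose-modification summary. The documents do not support that: any abnormality may be reported, and the exposure summary in 11.7 is independent of AE reporting. Nor can one say that an asymptomatic Grade 4 neutropenia managed by hold and reduction is not an AE, only that it need not be reported as one.

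What does not stand is that the reply closes the gap. Nearly every route in it runs through judgement, and the default instruction is not to report. The diagnosis route does not clearly cover an isolated cytopenia or transaminase rise, nor the chemistry changes that alone trigger action in Table 20. A SAP cannot restore a causality assessment that was never collected.

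**Conclusion.** The point holds as a gap in mandatory capture. Non-serious laboratory abnormalities that cause a hold, delay or reduction become AEs only at Investigator discretion, so the summaries of drug-related AEs and of AEs leading to dose modification may be incomplete and may vary by site or by known arm. This rests on the protocol text as it stands and assumes that no eCRF instruction already adds the trigger.

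The size is unknown. A reader might reach for the Phase 1 U2-V figures in Section 1.6: Grade 3 or higher neutropenia 21%, with AE discontinuations of 9% for umbralisib and 4% for venetoclax. Then 21 − (9 + 4) = 8 points, and 8 / 21 = 38%, is the least share of that neutropenia that led to discontinuation of neither drug. It does not measure under-reporting. The 21% is itself a rate of reported AEs in another study, and not all such neutropenia leads to a hold, since Table 22 keeps the dose at a first Grade 3 event. Any assumed reporting fraction, such as one half, would be a guess.

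**What to change.** Add to the mandatory triggers in 12.2.3.1, and to the eCRF guidance, any laboratory abnormality that leads to a hold, delay or dose reduction of any study drug. Add also any laboratory TLS, recorded as the diagnosis. Laboratory TLS criteria appear in the footnote to Table 23, where they describe earlier venetoclax data; the new text should say whether they apply. Sections 12.2.3.1, 8.5.4 and 11.9 would then agree.

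Do not make any treatment given for the abnormality a trigger. Table 22 suggests considering growth factor even for Grade 1–2 neutropenia, and Table 19 calls for routine TLS prophylaxis, so that wording would turn low-grade values and planned prevention into AEs.

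No dosing rule changes. The cost is a short addition to one section and its eCRF guidance, more AE records, and somewhat higher reported AE rates. It has to be made prospectively, because causality is assessed when the AE is recorded.
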